9.5 Medications to be used with caution: (a) CYP3A/CYP3A4 - Inhibitors//Inducers

Ibrutinib is metabolized primarily by CYP3A. Avoid co-administration with strong or moderate

CYP3A inhibitors and consider alternative agents with less CYP3A inhibition. Co-administration of ketoconazole, a strong CYP3A inhibitor, in 18 healthy subjects increased dose normalized exposure, Cmax and AUC0-last, of ibrutinib by 29- and 24-fold, respectively. The maximal observed ibrutinib exposure (AUC) was \leq 2-fold in 37 patients treated with mild and/or moderate CYP3A inhibitors when compared with the ibrutinib exposure in 76 patients not treated concomitantly with CYP3A inhibitors. Clinical safety data in 66 patients treated with moderate (n=47) or strong CYP3A inhibitors (n=19) did not reveal meaningful increases in toxicities. Strong inhibitors of CYP3A (e.g., ketoconazole, indinavir, nelfinavir, ritonavir, saquinavir, clarithromycin, telithromycin, itraconazole, and nefazadone) should be avoided. If a strong CYP3A inhibitor must be used, consider reducing ibrutinib dose to 140 mg or withhold treatment temporarily. Subjects should be monitored for signs of ibrutinib toxicity. If the benefit outweighs the risk and a moderate CYP3A inhibitor must be used, monitor subject for toxicity and follow dose modification guidance as needed. Avoid grapefruit and Seville oranges during ibrutinib treatment, as these contain moderate inhibitors of CYP3A. Co-administration of ibrutinib with strong CYP3A inducers, rifampin, in healthy subjects decreases ibrutinib plasma concentrations by approximately 10-fold. Avoid concomitant use of strong CYP3A inducers (e.g., carbamazepine, rifampin, phenytoin, and St. John's Wort). Consider alternative agents with less CYP3A induction. A comprehensive list of inhibitors, inducers, and substrates may be found at [REDACTED]. This website is continually revised and should be checked frequently for updates. (b) Drugs that may have their plasma concentrations altered by ibrutinib: *In vitro* studies indicated that ibrutinib is not a substrate of P-glycoprotein (P-gp), but is a mild inhibitor (with an IC50 of 2.15 μ g/mL). Ibrutinib is not expected to have systemic drug-drug interactions with P-gp substrates. However, it cannot be excluded that ibrutinib could inhibit intestinal P-gp after a therapeutic dose. There is no clinical data available; therefore, co-administration of narrow therapeutic index P-gp substrates (e.g., digoxin) with ibrutinib may increase their blood concentration and should be used with caution and monitored closely for toxicity. (c) QT prolonging agents: Any medications known to cause QT prolongation should be used with caution; periodic ECG and electrolyte monitoring should be considered. (d) Antiplatelet agents and anticoagulants: Warfarin or vitamin K antagonists should not be administered concomitantly with ibrutinib. Supplements such as fish oil and vitamin E preparations should be avoided. Use ibrutinib with caution in subjects requiring other anticoagulants or medications that inhibit platelet function. Subjects requiring the initiation of therapeutic anticoagulation therapy (eg, atrial fibrillation), consider the risks and benefits of continuing ibrutinib treatment. If therapeutic anticoagulation is clinically indicated, treatment with ibrutinib should be held and not be restarted until the subject is clinically stable and has no signs of bleeding. Subjects should be observed closely for signs and symptoms of bleeding. No dose reduction is required when study drug is restarted.

9.6 Prohibited concomitant medications:

Any chemotherapy, anticancer immunotherapy, experimental therapy, or radiotherapy are prohibited while the subject is receiving ibrutinib treatment. Corticosteroids for the treatment of the underlying disease (CLL) is prohibited. However, corticosteroids as pre-medication (and management of daratumumab related side effect) are allowed.

9.7a Management of Hepatitis B Virus Reactivation

Primary antiviral prophylaxis is permitted as per local standard of care. Per protocol, HBV DNA testing by PCR is mandatory for subjects at risk for HBV reactivation. For subjects who develop HBV reactivation while on study treatment, study treatment should be suspended and any concomitant steroids, chemotherapy, and institute appropriate treatment. Resumption of study treatment in patients whose HBV reactivation is adequately controlled. If the benefits outweigh the risks, study treatment may be resumed with concomitant antiviral prophylaxis as per local standard of care. Consult a liver disease specialist as clinically indicated.

9.7b Prophylaxis for Herpes Zoster Reactivation:

Prophylaxis for herpes zoster reactivation is recommended during the Treatment Phase, as per institutional guidelines. Initiate antiviral prophylaxis to prevent herpes zoster reactivation within 1 week after starting study treatment and continue for 3 months following study treatment. Acceptable antiviral therapy includes acyclovir (eg 400 mg given orally 3 times a day, or 800 mg given orally 2 times a day or per institutional standards), famcyclovir (eg, 125 mg given orally, twice a day or per institutional standards), or valacyclovir (eg, 500 mg given orally, twice a day or per institutional standards), initiated within 1 week after the start of study drug.

9.8 Guidelines for ibrutinib management with surgeries or procedure:

Ibrutinib may increase the risk of bleeding with invasive procedures or surgery. Consider the benefit- risk of withholding ibrutinib for at least 3 to 7 days pre and post-surgery depending upon the type of surgery and the risk of bleeding. The following guidance may be applied to the use of ibrutinib in the perioperative period for patients who require surgical intervention or an invasive procedure while receiving ibrutinib: (a) Minor surgical procedures - For minor procedures (such as a central line placement, needle biopsy, thoracentesis, or paracentesis) ibrutinib should be held for 3 days prior to the procedure and should not be restarted for at least 3 days after the procedure. For bone marrow biopsies that are performed while the subject is on ibrutinib, it is not necessary to hold ibrutinib for these procedures. (b) Major surgical procedures - For any surgery or invasive procedure requiring sutures or staples for closure, ibrutinib should be held at least 7 days prior to the intervention and should be held at least 7 days after the procedure and restarted at the discretion of the investigator when the surgical site is reasonably healed without serosanguineous drainage or the need for drainage tubes. (c) Emergency Procedures - For emergency procedures, ibrutinib should be held after the procedure until the surgical site is reasonably healed, for at least 7 days after the urgent surgical procedure.

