Overall design: This is a phase II clinical trial of two novel drugs (daratumumab and hyaluronidase given SC and ibrutinib given orally) for treatment of patients with relapsed or refractory CLL. During the first cycle of the treatment, patients are given daratumumab as a single agent (for conduct of correlative studies – please see section 7.0), and starting cycle 2 patients will have both ibrutinib and daratumumab given together. Patients will be grouped in independent cohorts based upon whether they previously received a BTK inhibitor (Cohort 1) vs. BTK inhibitor naïve (Cohort 2). A total of 52 eligible patients will be enrolled in two separate cohorts (i.e. Cohort 1 and 2). A total of 25 cycles (including the first cycle with single agent daratumumab) will be given. The primary goal is to determine ORR of this regimen in each arm.

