3.2 Registration - Exclusion Criteria

3.21 Any serious medical condition, laboratory abnormality, or psychiatric illness that would prevent the subject from signing the informed consent form.

3.22 Patient is known to have **chronic obstructive pulmonary disease** with a forced expiratory volume in 1 second (FEV1) $<50\%$ of predicted normal (Note: FEV1 testing is required for subjects suspected of having chronic obstructive pulmonary disease and subjects must be excluded if FEV1 $<50\%$ of predicted normal.)

3.23 Patient is known to have **moderate or severe persistent asthma** within the past 2 years, or currently has uncontrolled asthma of any classification (Note: subjects who currently have controlled intermittent asthma or controlled mild persistent asthma are allowed in the study.)

3.24 Since this study involves an investigational agent whose genotoxic, mutagenic and teratogenic effects on the developing fetus and newborn are unknown, any of the following will deem the subject ineligible for the study:

- Pregnant women
- Nursing women
- Men or women of childbearing potential who are unwilling to employ adequate contraception

3.25 Any condition, including the presence of laboratory abnormalities, which places the subject at unacceptable risk if he/she were to participate in the study or confounds the ability to interpret data from the study.

3.26 Patients who have received **no prior therapy** for CLL.

3.27 Patients with history of any other cancer (except non-melanoma skin cancer or carcinoma in-situ of the cervix, unless in complete remission and off therapy for that disease for >3 years).

3.28 Patients who have **previously received daratumumab or any other anti-CD38 therapy** on a clinical trial or for any other malignancy.

3.29 Prior or current exposure to any of the following:

- Exposure to an investigational drug (including investigational vaccine) or invasive investigational medical device for any indication within 4 weeks or 5 pharmacokinetic half-lives, whichever is longer.
- Focal radiation therapy within 14 days prior to randomization with the exception of palliative radiotherapy for symptomatic management but not on measurable extramedullary plasmacytoma

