4.0 Test Schedule

4.1 Test schedule for Relapsed / Refractory Chronic Lymphocytic Leukemia

Tests & Procedures	Active Monitoring Phase				
	Prior to Registration		Cycle 1 Day 1	Cycle 1 Day 15	Prior to subsequent Treatment (Cycles 2 – and 24 , Day 1) ¹⁴
Window	≤ 28 days	≤ 14 days			3-4 weeks from the last dose of treatment
Complete medical history (including prior treatment regimen)	X				
Adverse event assessment	X		X		X
Physical exam, including weight and vital signs, and PS		X	X		X
Clinical Response assessment (Tumor measurement by physical exam) ^{1,2}		X			X
CT scans (Chest, Abdomen, Pelvis) ³	X				X
EKG/ECHO ⁴	X				
CBC with differential ⁵		X	X	X	X
Chemistry group (SGOT [AST], SGPT [ALT], serum creatinine, direct bilirubin ¹³ and total bilirubin, LDH, uric acid, phosphorus, alkaline phosphate, sodium potassium,) ⁵		X	X	X	X
Quantitative Immunoglobulins ⁶	X				X
Minimal residual disease assessment ⁷	X			X	X ¹⁵

Flow Cytometry-CLL Panel ⁸	X					
Bone marrow biopsy and/or aspirate ⁹	X				X	X
CLL FISH Panel ¹⁰	X					
B2M, Zap 70, CD38, IgHV ¹¹	X					
Urine/blood Pregnancy test ¹³		X				
Hepatitis B (HBV) serology ¹⁶	X					
HBV DNA testing ¹⁷	X		X ¹⁷		X ¹⁷	X ¹⁷
Dara and Ibrutinib ¹⁸			X	X	X	

1. The physical exam should measure the spleen and liver, noting the maximal distance below the respective costal margins and should record the bi- dimensional diameter of the largest palpable node in each area of involvement including the following sites: left neck (sub-mandibular, cervical, supra-clavicular), right neck (sub-mandibular, cervical, supra-clavicular), left axillary, right axillary, left groin (inguinal, femoral) and right groin (inguinal, femoral).
2. Clinical response assessment: will be done per IWCLL criteria starting with evaluation of disease state at baseline and then at the end of Cycle 1 and every 3 cycles during combination treatment and at the end of treatment.
3. CT scans should be done as clinically indicated for the management of the patient and in accordance with the IWCLL guidelines. CT scans may be done with patient's primary physician (if outside Mayo Clinic), results of these will be entered in the source document.
4. EKG or ECHO only if clinically indicated.

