7.0 Protocol Treatment

Overall Treatment Schedule: Overall treatment schedule (for both Cohorts) include patient receiving Daratumumab SC alone in C1 followed by addition of ibrutinib to daratumumab starting C2 (and onwards). For patients already on BTK inhibitor who are entering Cohort 1, BTK inhibitor will be stopped (see also note below for more detailed clarification) for at least 1 week prior (washout period) to initiating C1 (daratumumab alone). Once these patients have completed the C1, ibrutinib will be started as part of the combination regimen starting C2.

Note: Treatment can be initiated/continued independent of disease activity during the washout period i.e. if the disease is progressing while on Daratumumab alone. Also, given the clinical course of patients resistant to BTK inhibitor can be rapid, if in treating physician opinion stopping the BTK inhibitor can impact adversely patient's disease course than patient may continue the BTK inhibitor up until starting study treatment and then Ibrutinib plus daratumumab will be started in lieu of BTK inhibitor. In such a case, Cycle 1 will have both ibrutinib + Daratumumab. The schedule and dosing of Daratumumab will follow the same design as noted in 7.2. This, however must be approved by the Principal Investigator [REDACTED] of the study protocol.

Duration of treatment: Patient will be treated as indicated in section 7.0, unless they have progressive disease or unacceptable toxicity. Patients who complete treatment per protocol will continue to the end of treatment visit and then, survival follow-up.

DARATUMUMAB

7.1 Daratumumab Subcutaneous schedule (Cycle length = 28 days, ± 4 days):

- **Cycle 1 & 2:** Daratumumab SC alone (1800 mg dose) weekly (Days 1, 8, 15, 22 of each cycle).
- **Cycle 3-6:** Daratumumab SC (1800 mg dose) will be given every 2 weeks (Days 1, 15 of each cycle).
- **Cycle 7 onwards:** Daratumumab SC (1800 mg dose) will be given every 4 weeks (Day 1 of each cycle).

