8.1 Dose Levels (Based on Adverse Events in Tables 8.2 and 8.3)

Dose Level	Ibrutinib
1*	420 mg daily
-1	280 mg daily
-2	140 mg daily

*Dose level 1 refers to the starting dose.

NOTE: If either of Daratumumab or Ibrutinib is discontinued, the patient can continue on the other drugs, unless specified otherwise in the dose modification tables. If both are discontinued, the patient will go to survival follow-up (Section 4.2). No dose modifications are allowed for daratumumab

→ → Use the NCI Common Terminology Criteria for Adverse Events (CTCAE) current version 5.0* unless otherwise specified ← ←

*Located at [REDACTED]

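### The radiotherapy rules in 3.29 and 9.6 protect a myeloma lesion and start with ibrutinib, so a CLL response site could be irradiated after baseline without breaking a named rule

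*Combined protocol and SAP*

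**What the plan says.** **Before entry.** Section 3.29 excludes: "Focal radiation therapy within 14 days prior to randomization with the exception of palliative radiotherapy for symptomatic management but not on measurable extramedullary plasmacytoma". Palliative radiotherapy is thus exempt, except to one kind of lesion. The look-back is counted from randomization, but patients are registered into two cohorts by prior BTK inhibitor use (5.1) and nobody is randomized.

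**On study.** Section 9.6 states: "Any chemotherapy, anticancer immunotherapy, experimental therapy, or radiotherapy are prohibited while the subject is receiving ibrutinib treatment". The same section also says "Corticosteroids for the treatment of the underlying disease (CLL) is prohibited", and that sentence has no ibrutinib limit.

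**When ibrutinib starts.** Section 7.0 prescribes "Daratumumab SC alone in C1 followed by addition of ibrutinib to daratumumab starting C2", and 7.9a gives Day 1 of Cycle 2. There is one exception in 7.0: with the Principal Investigator's approval, a patient already on a BTK inhibitor may take ibrutinib with daratumumab from Cycle 1.

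**Baseline and response.** The test schedule (4.1) places "Clinical Response assessment (Tumor measurement by physical exam" within 14 days before registration, and CT within 28 days. Treatment must start within 14 days after registration (6.5). Partial response uses nodes (11.222), liver or spleen (11.223) and, for patients measurable only on CT, target nodes (11.227).

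**The concern.** Both rules exist so that other anticancer treatment does not alter the disease being measured. Section 3.29 appears to be carried over from a myeloma protocol; 8.2 likewise still names myeloma drugs and underlying myeloma. In its source the clause would have protected the measured lesion. Here it protects nothing on which CLL response is scored. Section 9.6 then begins only with ibrutinib.

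The uncovered weeks are ones in which local symptoms are plausible. Section 7.0 stops a current BTK inhibitor at least a week before Cycle 1, recognises that BTK-resistant disease can move fast, and lets treatment go on if disease progresses on daratumumab alone.

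At stake is a response credited to the regimen that radiotherapy produced. Nodes and liver or spleen are two of the three main features of partial response. The third, the lymphocyte count, drops out during ibrutinib lymphocytosis (11.221), which puts more weight on the two that radiotherapy can shrink.

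**Working it through.** **1. Coverage by period, default schedule**

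| Period | Rule that names radiotherapy | CLL response site protected? |
|---|---|---|
| Days 28 to 15 before registration, after a baseline CT | None | No |
| Days 14 to 0 before registration | 3.29: non-palliative focal radiotherapy excluded, palliative exempt | Not from palliative radiotherapy |
| Registration to first dose | None | No |
| Cycle 1, daratumumab alone | None | No |
| From Cycle 2 Day 1, on ibrutinib | 9.6 | Yes |

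Under the 7.0 exception the 9.6 ban applies from first dose, so for those patients the Cycle 1 row closes.

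**2. Length of the window**

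Inputs: baseline exam up to 14 days and CT up to 28 days before registration (4.1); up to 14 days from registration to treatment (6.5); Cycle 1 of 28 days (7.1).

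- Registration to first ibrutinib: 0 + 28 = 28 days at least, 14 + 28 = 42 at most.
- Baseline exam to first ibrutinib: at most 14 + 14 + 28 = 56 days.
- Baseline CT to first ibrutinib, CT-only disease: at most 28 + 14 + 28 = 70 days.
- The cycle tolerance of 4 days either way moves each figure by up to 4.

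These are windows, not probabilities.

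**3. The plan's own operating characteristics**

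These are exact binomial upper tails.

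- Cohort 1 (16.21): P(X ≥ 3 | n = 22, p = 0.05) = 0.0948 and P(X ≥ 3 | 22, 0.20) = 0.8455. The plan prints 0.09 and 0.85.
- Cohort 2 (16.22): P(X ≥ 17 | 26, 0.50) = 0.0843 and P(X ≥ 17 | 26, 0.75) = 0.9091. The plan prints 0.08 and 0.91.

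Both designs reproduce.

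**4. Scenario: exactly one falsely credited patient, null true otherwise**

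One success is fixed, so the other patients need one fewer.

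- Cohort 1: P(X ≥ 2 | 21, 0.05) = 0.2830.
- Cohort 2: P(X ≥ 16 | 25, 0.50) = 0.1148.

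**5. Range under an assumed frequency**

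Let r be the chance that one such patient occurs in the cohort. The documents give no r, so the values below are assumptions. The probability of declaring promise under the null is (1 − r) × (step 3) + r × (step 4).

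| r | Cohort 1 | Cohort 2 |
|---|---|---|
| 0 | 9.5% | 8.4% |
| 5% | 10.4% | 8.6% |
| 10% | 11.4% | 8.7% |
| 20% | 13.2% | 9.0% |

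**The case against.** The case on the other side is substantial, and much of it stands.

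- **A false credit needs several things at once.** Section 11.22 requires two features (if abnormal) plus a blood-count criterion for two months. Nodes are scored as a sum across regions, so one irradiated node matters only if it dominates that sum. The effect must also last to the assessment after six combination cycles. This stands, and it is why the frequency is probably low.
- **Early shrinkage may be seen.** A physical exam is scheduled on Cycle 1 Day 1, with nodes, liver and spleen to be measured (4.1, footnote 1), and a response assessment follows Cycle 1 (11.0). This stands as a chance of detection. It does not reset the baseline.
- **The 7.0 exception covers some of the patients most likely to need radiotherapy.** It does so from first dose, and only with approval.
- **Other provisions might catch it.** Section 3.25 allows exclusion for anything that confounds interpretation, but it is discretionary and applies at entry. Section 13.7 needs a severe violation of Cycle 1 treatment requirements, and none of these names radiotherapy. Neither closes the gap.

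Three stronger readings are tempting, and the documents do not support them. A reader might infer that any other CLL therapy is open in Cycle 1. But in that cycle "patients are given daratumumab as a single agent" (1.3), CLL-directed steroids are barred throughout, and 3.29 also excludes recent "Exposure to an investigational drug (including investigational vaccine" use. The single-agent wording describes the drug regimen, so only radiotherapy is left unaddressed. A reader might also point to 8.1, "If either of Daratumumab or Ibrutinib is discontinued, the patient can continue on the other drugs", as a second gap after ibrutinib stops. But 16.311 counts response after six combination cycles and 16.321 counts it during combination treatment, so that period has little route to either endpoint. Finally, 16.323 handles other CLL treatment for progression-free survival while the response sections have no such rule. It does not follow that irradiated patients must be scored as non-responders. That is a debatable scoring choice, and the gap can be closed without it.

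**Conclusion.** The point holds and is minor. On the default schedule no rule naming radiotherapy applies from registration to Cycle 2 Day 1 (28 to 42 days). Before registration, palliative radiotherapy to a CLL response site is not excluded. It is more than a clerical slip, because working eligibility and concomitant-treatment rules protect the wrong lesion and the wrong period.

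The 28.3% should not be read as the trial's false-positive rate. It assumes that one falsely credited responder already exists. If the chance of such a patient is taken as 5% to 20%, the Cohort 1 figure is 10.4% to 13.2%, and Cohort 2 hardly moves. Nor do the documents authorise or anticipate radiotherapy to a response site on study. They are silent, and silence is what needs correcting. The concern is greatest for patients whose nodes or spleen are the main abnormal feature, or whose disease is measurable only on CT, and for Cohort 1 because so few responses decide it.

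**What to change.** 1. **Section 3.29.** Replace the plasmacytoma phrase with *any node or organ used for response assessment*. Replace the look-back from randomization with *in the 14 days before registration, or after the baseline exam or CT used for response if that is earlier*. A patient irradiated at a response site before registration needs a new baseline. Palliative radiotherapy to other sites before registration stays allowed.
2. **Section 9.6.** Replace the clause tying the ban to ibrutinib with *from registration until the end of protocol treatment (daratumumab or ibrutinib)*. Leave the period before registration to 3.29, so that the two rules do not overlap, and keep the 7.0 allowance for a continuing BTK inhibitor.

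Cost: wording only, with no change to sample size or decision rules. An occasional patient is delayed or re-baselined before entry. A patient who needs radiotherapy to any site during Cycle 1 comes off protocol treatment, as 9.6 already implies from Cycle 2. One who needs it between registration and first dose could not start. No scoring rule for irradiated patients needs to be added.
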